A Phase II Clinical Trial Examining The Impact Of Neoadjuvant Axitinib On Primary Tumor Response In Patients With Locally Advanced Clear Cell Renal Cell Carcinoma

Principle Investigator: [name], M. D., FACS
Associate Professor and Deputy Chairman
Department of Urology
The University of Texas M. D. Anderson Cancer Center

Co-Principle Investigator: [name].
Assistant Professor
Department of Urology
The University of Texas M. D. Anderson Cancer Center

Collaborators: [name], M. D.
Associate Professor
Department of Urology
The University of Texas M. D. Anderson Cancer Center

[name], M. D.
Associate Professor
Department of Genitourinary Medical Oncology
The University of Texas M. D. Anderson Cancer Center

[name], M. D.
Associate Professor
Department of Genitourinary Medical Oncology
The University of Texas M. D. Anderson Cancer Center

[name], M. D.
Associate Professor
Department of Pathology
The University of Texas M. D. Anderson Cancer Center

[name], M. D.
Assistant Professor
Department of Diagnostic Radiology
The University of Texas M. D. Anderson Cancer Center

[name].
Associate Professor
Department of Diagnostic Radiology
The University of Texas M. D. Anderson Cancer Center

[name], M.S.
Senior Statistical Analyst
Division of Quantitative Sciences
The University of Texas M. D. Anderson Cancer Center

[name], R.N.
Research Nurse Supervisor
Department of Urology
The University of Texas M. D. Anderson Cancer Center

SYNOPSIS

Primary Objective:

Assess objective response rate following the administration of axitinib for 12 weeks in patients with locally advanced biopsy-proven clear cell renal cell carcinoma prior to undergoing radical nephrectomy.

Secondary Objectives:

- Study the safety, tolerability, and feasibility of the administration of axitinib in patients with locally advanced biopsy-proven clear cell renal cell carcinoma prior to undergoing radical nephrectomy.
- Assess disease-free survival and overall survival in patients with locally advanced biopsy proven clear cell renal cell carcinoma treated with 12 weeks of neoadjuvant axitinib followed by radical nephrectomy.
- Collect renal tissue, blood (serum, plasma, DNA, and PBMC), and urine for future correlative biomarker studies.

Table of Contents

1. Background and Rationale
2. Protocol drug
 - 2.1. Axitinib
 - 2.1.1. Dosage
 - 2.1.2. Pharmacokinetics and Pharmacodynamics
 - 2.1.3. Side Effects Profile

Axitinib, a novel oral tyrosine kinase inhibitor of VEGFR-1, VEGFR-2, and VEGFR-3 has been recently investigated in 52 patients with metastatic ccRCC who failed prior systemic therapy with Interferon- α or Interleukin-2 ⁷. Responses were seen in 23 patients (44.2%), with two patients achieving complete response and one patient without prior nephrectomy having partial shrinkage of the primary renal tumor. Axitinib has also been investigated in 62 patients with metastatic ccRCC refractory to sorafenib ⁸, and partial response was observed in 22.6% of patients, with 80% experiencing some degree of tumor shrinkage. As such, axitinib appears to be a promising agent in the treatment of metastatic ccRCC.

We will be using the tyrosine kinase inhibitor axitinib up to 36 hours prior to radical nephrectomy in order to maximize the exposure time and potential benefit from this drug. This approach has been shown to be safe. Recently, Hellenthal et al ⁹ reported on a prospective trial of 3 months of the tyrosine kinase inhibitor sunitinib in 20 patients with renal cell carcinoma prior to radical nephrectomy. In 15 patients, sunitinib was stopped 1 day prior to surgery, and no surgical complications were attributable to sunitinib treatment. This is consistent with our experience ¹⁰, as we have not found a significant difference in surgical complications when comparing patients who received targeted therapy prior to radical nephrectomy with those who have not received any preoperative therapy.

Neoadjuvant therapy in the non-metastatic setting has the potential of improving overall survival, as seen from trials in non-metastatic bladder cancer ¹¹. To date, there are no published prospective trials of neoadjuvant targeted therapy prior to radical nephrectomy in patients without metastases. The use of axitinib in patients with ccRCC prior to radical nephrectomy has the potential of decreasing tumor size (which might allow us to perform a partial nephrectomy rather than a radical nephrectomy-thereby preserving renal function), regression of invasion into adjacent organs, regression of tumor venous thrombi, therefore improving surgical margins and treatment outcomes. In addition, collection of blood and tissue for molecular and genetic analysis is possible using this neoadjuvant approach, which will provide valuable information about molecular correlates of tumor response to

targeted therapy. Finding molecular correlates of activity or resistance to axitinib will allow us in future trials to select the appropriate patients to receive neoadjuvant therapy.

2. Protocol Drug

2.1. Axitinib

2.1.1. Dosage

Axitinib is given orally at a starting dose of 5mg twice daily (BID) with food. Dosage modifications will be discussed below.

2.1.2. Pharmacokinetics and Pharmacodynamics

Axitinib administered in the fed state is absorbed rapidly, with peak plasma concentrations occurring within 2 to 6 hours. Plasma concentrations declined with a terminal plasma half-life between 2 and 5 hours. Axitinib plasma PK reached steady state within 15 days. At the phase II dose of 5 mg BID given in the fasted state, the between-patient coefficient of variation for AUC_{0-24} on cycle 1, day 15 was 90%; the corresponding coefficient of variation for C_{max} was 63%. Both the rate and extent of absorption were higher in the fasted state. Peak concentrations occurred 1 to 2 hours after dosing in the fasted state, and there was a median 49% increase in plasma exposures compared with the fed state. Plasma half-life was not changed appreciably in fed and fasted states.

In the presence of the potent proton-pump inhibitor rabeprazole, the rate of absorption of axitinib was decreased, but the extent of absorption was unaffected. Because of the minimal change in plasma exposure in the presence of rabeprazole, the effect of antacids on axitinib absorption was not considered to be clinically significant.

Twelve-hour urinary collections obtained on days 1 and 29 (cycle 2, day 1) demonstrated that < 1% of the administered dose appeared as unchanged drug in the urine regardless of dose, which indicates that the majority of drug elimination was through systemic metabolism.

Soluble plasma proteins (VEGF, fibroblast growth factor, tumor necrosis factor- α , and matrix metalloproteinases 2 and 9) evaluated as exploratory markers related to VEGFR signal transduction pathways did not show any variation with treatment.

2.1.3. Side Effects Profile

The most common side effects (all grades) are hypertension, diarrhea, fatigue, nausea, hoarseness, anorexia, dry skin, and weight loss.

3. Inclusion and Exclusion Criteria

3.1. Study Population

A total of 24 patients with clear cell renal cell carcinoma clinical stage T2-T3bN0M0 will be treated in this study with an estimated accrual of 3 patients per month. Please see section 6 for statistical considerations. We will enroll additional patients to allow for screen failures after biopsy results, or patient withdrawal.

3.2. Inclusion Criteria

- 3.2.1. Locally advanced renal cell carcinoma without evidence of metastatic disease with absence of adjacent organ invasion or retroperitoneal adenopathy (cT2-T3b, N0, M0). Patients with retroperitoneal lymph nodes ≤ 2 cm in size each are considered N0.
- 3.2.2. Predominant clear cell histology on pre-treatment biopsy of the primary tumor.
- 3.2.3. Patient should be candidate for curative radical nephrectomy.
- 3.2.4. ECOG Performance Status 0-1.
- 3.2.5. Patient must provide signed informed consent.
- 3.2.6. Male or female, age ≥ 18 years.
- 3.2.7. Adequate renal function: serum creatinine level $\leq 1.5 \times$ ULN or calculated creatinine clearance (as estimated by GFR using the MDRD formula) is ≥ 60 ml/min.
- 3.2.8. Adequate hepatic function: alkaline phosphatase $\leq 1.5 \times$ ULN; total bilirubin, AST, and ALT $\leq 1.5 \times$ ULN; INR <1.3 (or <3 if on anticoagulant therapy).
- 3.2.9. Adequate bone marrow function: ANC $\geq 1.5 \times 10^9/L$; Platelets $\geq 100 \times 10^9/L$; Hb >9 g/dL.
- 3.2.10. Urinary protein <100 on urinalysis (equivalent to $<2+$ by urine dipstick). If urinalysis protein ≥ 100 (equivalent to dipstick is $\geq 2+$) then a 24-hour urine collection can be done and the patient may enter only if urinary protein is <2 g per 24 hours.
- 3.2.11. No hormonal therapy, chemotherapy, immunotherapy, or any other systemic therapy for a malignancy in the 5 years prior to current study enrollment.
- 3.2.12. Women of childbearing potential (defined as a female subject who is not surgically sterilized, not at least 1 year postmenopausal) must have negative urine or serum

pregnancy test within 4 weeks of enrollment and again on the day of starting therapy and she and/or her partner must utilize birth control while on therapy.

3.2.13. Male (defined as a male subject who has not been surgically sterilized) or female patients of child-producing potential must agree to use adequate contraception (e.g. IUD, condom plus spermicide, diaphragm, or cervical cap plus spermicide) or medical contraception as of date of study enrollment and for 1 month after last dose of axitinib. Subjects who are not currently sexually active must agree and consent to use one of the above-mentioned methods should they become sexually active while participating in the study.

3.3. Exclusion Criteria

- 3.3.1. Evidence of metastatic disease, adjacent organ invasion, retroperitoneal adenopathy on pre-treatment imaging. In addition, patients with inferior vena cava thrombi extending to the atrium or with evidence of Budd-Chiari Syndrome (hepatic dysfunction) will not be eligible for the protocol.
- 3.3.2. Patients who undergo embolization of their primary tumor
- 3.3.3. Previous treatment for their primary renal tumor, including prior chemotherapy, immunotherapy, targeted therapy, radiation therapy, cryotherapy, radiofrequency ablation or embolization.
- 3.3.4. Active malignancies other than renal cell carcinoma and/or history of other malignancy within the last 5 years, except for adequately treated cone-biopsied in situ carcinoma of the cervix or basal or squamous cell carcinoma of the skin.
- 3.3.5. Uncontrolled hypertension (BP>140/90 on medications) as documented by 2 baseline blood pressure readings taken at least 1 hour apart. The baseline systolic blood pressure readings must be ≤ 140 mm Hg, and the baseline diastolic blood pressure readings must be ≤ 90 mm Hg. Patients whose hypertension is controlled by antihypertensive therapies are eligible.
- 3.3.6. Current use or anticipated need for treatment with drugs that are known potent CYP3A4 inhibitors (ie, grapefruit juice, verapamil, ketoconazole, miconazole, itraconazole, erythromycin, telithromycin, clarithromycin, indinavir, saquinavir, ritonavir, nelfinavir, nefazodine, lopinavir, atazanavir, amprenavir, fosamprenavir and delavirdine).

- 3.3.7. Current use or anticipated need for treatment with drugs that are known potent CYP3A4 or CYP1A2 inducers (ie, carbamazepine, dexamethasone, felbamate, omeprazole, phenobarbital, phenytoin, amobarbital, nevirapine, primidone, rifabutin, rifampin, and St. John's wort).
- 3.3.8. Active gastrointestinal bleeding.
- 3.3.9. Malabsorption syndromes such as celiac disease, cystic fibrosis, inflammatory bowel disease, systemic sclerosis, and carcinoid syndrome.
- 3.3.10. Known HIV or Hepatitis C status.
- 3.3.11. Requirement of anticoagulant therapy with oral vitamin K antagonists. Low-dose anticoagulants for maintenance of patency of central venous access device or prevention of deep venous thrombosis is allowed. Therapeutic use of low molecular weight heparin is allowed.
- 3.3.12. Active seizure disorder or evidence of brain metastases, spinal cord compression, or carcinomatous meningitis.
- 3.3.13. A serious uncontrolled medical disorder or active infection that would impair their ability to receive study treatment.
- 3.3.14. Any of the following within the 12 months prior to study drug administration: myocardial infarction, uncontrolled angina, coronary/peripheral artery bypass graft, symptomatic congestive heart failure, cerebrovascular accident or transient ischemic attack and 6 months for deep vein thrombosis or pulmonary embolism
- 3.3.15. Withdrawal of consent.
- 3.3.16. Unwillingness or inability to comply with mandated pre-treatment biopsy or therapeutic regimen.

4. Trial Objectives

4.1. Primary Objective

Assess objective response rate following the administration of axitinib for 12 weeks in patients with locally advanced biopsy-proven clear cell renal cell carcinoma prior to undergoing radical nephrectomy.

4.2. Secondary Objectives

- 4.2.1. Study the safety, tolerability, and feasibility of Axitinib in patients with locally advanced biopsy-proven clear cell renal cell carcinoma prior to undergoing radical nephrectomy.
- 4.2.2. Assess disease-free survival and overall survival in patients with locally advanced biopsy proven clear cell renal cell carcinoma treated with 12 weeks of neoadjuvant Axitinib followed by radical nephrectomy.
- 4.2.3. Collect renal tissue, blood (serum, plasma, DNA, and PBMC), and urine for future correlative biomarker studies.

5. Assessment of Response

CT scans of the chest and abdomen will be evaluated by a urologist and an expert genitourinary radiologist. The urologist (investigator assessment) and the radiologist (independent assessment) will perform the tumor measurements. Response will be determined by the radiologist assessment. Tumor measurements will be documented in the tumor measurement form (one of the CRFs) and medical record. GURU will be used as electronic case report forms (CRF). RECIST version 1.0 criteria will be used as follows to quantify response to therapy:

- Complete Response (CR): Complete disappearance of renal mass.
- Partial Response (PR): At least a 30% decrease in the largest diameter (LD) of the renal mass taking as reference the baseline largest diameter.
- Progressive disease (PD): At least a 20% increase in the LD of the renal mass taking as reference the LD of the renal mass recorded since the treatment started. PD will also include development of any biopsy-proven metastatic disease.
- Stable Disease (SD): Neither sufficient shrinkage to qualify for PR nor sufficient increase to qualify for PD taking as reference the LD since the treatment started.
- Objective response rate (ORR) is defined as CR+PR.
- ORR will be evaluated when CT abdomen is done after 12 weeks of treatment (see Table 4).
- PD will be evaluated when CT abdomen is done after 7 weeks and 12 weeks of treatment (see Table 4).

6. Statistical Considerations

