6.1. Statistical Considerations for Primary Objective

The primary objective of this study is to assess objective response rate (ORR) following the administration of axitinib for 12 weeks in patients with locally advanced biopsy-proven clear cell renal cell carcinoma prior to undergoing radical nephrectomy.

Twenty-four patients will be treated in this study. We plan to abort recruitment should we have reason to believe that axitinib does not provide minimal efficacy, defined as $\Pr[\text{ORR} \geq 20\% \mid \text{data}] < 5\%$. We also plan to stop recruitment should we have reason to believe that it may be harmful, defined as $\Pr[\text{PD} > 20\% \mid \text{data}] > 80\%$, where PD is progressive disease. We will monitor study patients using the Bayesian approach of Thall¹². ORR will be evaluated at week 12 following initiation of treatment and PD will be evaluated at week 7 and week 12 following initiation of treatment.

For calculating our stopping criteria and operating characteristics for futility and disease progression, we assume that $\text{ORR} \sim \text{Beta}(0.4, 1.6)$ and $\text{PD} \sim \text{Beta}(0.4, 1.6)$. The prior for both ORR and PD has a mean of 20% and a standard deviation of 23%.

We will continually evaluate patients for excessive PD as they are being enrolled. We will begin evaluating for minimal ORR after the first 18 patients have been treated and evaluated for responses. Given that those patients who have PD will be immediately terminated from the study treatment to have a nephrectomy, we do not feel that delaying evaluation for futility until 18 patients are treated will jeopardize patient wellbeing. Once the minimum number of patients has been treated and assessed for ORR and PD, we will continue to assess both outcomes after each additional patient has been evaluated.

The trial will be stopped for futility (low ORR) if

$$[\# \text{ of patients with ORR} / \# \text{ of patients evaluated at Week 12}] \leq 1/18.$$

Likewise, the trial will be stopped for excessive PD if

$$[\# \text{ of patients with PD} / \# \text{ of patients evaluated at Week 7 and 12}] \geq 3/6, 4/9, 5/13, 6/17, 7/21.$$

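### Does Section 5 need a precedence rule for a patient who meets both CR/PR and PD at week 12?

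*Combined protocol and SAP*

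**What the plan says.** The title describes the trial as examining the "Impact Of Neoadjuvant Axitinib On Primary Tumor Response". Section 5 then sets the classes:

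- CR: "Complete disappearance of renal mass".
- PR: "At least a 30% decrease in the largest diameter (LD) of the renal mass taking as reference the baseline largest diameter".
- PD by size: growth of 20% or more, "taking as reference the LD of the renal mass recorded since the treatment started".
- PD by spread: "PD will also include development of any biopsy-proven metastatic disease".
- SD: whatever reaches neither the PR nor the PD size limit.
- "Objective response rate (ORR) is defined as CR+PR", read on the week-12 abdominal CT. PD is read at weeks 7 and 12.
- "Response will be determined by the radiologist assessment".

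Section 6.1 sets separate rules for ORR and PD and says that, once monitoring of both has begun, "we will continue to assess both outcomes after each additional patient has been evaluated". It also says that patients with PD come off study treatment at once and go to nephrectomy. Section 7.2.12 classes progression at week 7, in the primary or as metastasis, as treatment failure.

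**The concern.** CR and PR carry no condition about disease outside the kidney, ORR carries no exclusion for PD, and only SD is defined by ruling out other classes. Two kinds of patient could therefore hold two classes at week 12.

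- **Route 1, new metastasis.** The renal mass has shrunk by at least 30% from baseline, and a metastasis is found and proven by biopsy.
- **Route 2, regrowth.** PR is measured from baseline, while the PD wording does not say whether its reference is the baseline, week-7 or smallest diameter. If it is the week-7 value, a tumour that shrinks strongly and then regrows can be PR and PD together.

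ORR is the primary endpoint. It drives the futility rule (1/18) and the success rule (7 or more of 24), so the status of one patient could decide the trial's conclusion. A choice made after seeing six or seven responders would be open to challenge.

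**Working it through.** **Inputs.** From Section 6.1: prior Beta(0.4, 1.6), n = 24, first futility look at 18 patients, futility if Pr[ORR ≥ 20%] < 5%, success if Pr[ORR > 20%] > 80%. From Section 5: the 30% and 20% size limits.

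**1. The plan's own rules.** With x responders among n, the posterior is Beta(0.4 + x, 1.6 + n − x).

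| x/n | Pr[ORR > 20%] | Result |
|---|---|---|
| 7/24 | 0.831 | success |
| 6/24 | 0.688 | not success |
| 2/18 | 0.134 | continue |
| 1/18 | 0.033 | stop |

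Both cut-offs reproduce. The PD bounds (3/6, 4/9, 5/13, 6/17, 7/21) reproduce too. Exact stopping probabilities agree with Tables 1 and 2 to within 0.01; for example, Table 1 at a rate of 0.20 is 0.099 by exact calculation against 0.106 stated. None of this depends on how a patient in both classes is labelled.

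**2. Can the overlap occur?**

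- Route 1: 10 cm to 6.8 cm is 6.8/10 − 1 = −32% (PR). A biopsy-proven metastasis makes the patient PD as well.
- Route 2: 10, 5.5 and 6.8 cm at baseline, week 7 and week 12. From baseline the change is −32% (PR). From week 7 it is 6.8/5.5 − 1 = +23.6% (PD). The week-7 diameter must be at most 0.70/1.20 = 0.583 of baseline, a shrinkage of at least 41.7%. If baseline is the PD reference, PR needs a ratio of at most 0.70 and PD one of at least 1.20, so they cannot coincide.

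**3. Effect if one such patient occurs.** The other 23 patients respond as Binomial(23, p). If the patient is counted, success needs 6 or more of the 23; if not, 7 or more.

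| p | Counted | Not counted |
|---|---|---|
| 0.20 | 0.305 | 0.160 |
| 0.25 | 0.531 | 0.346 |
| 0.30 | 0.731 | 0.560 |

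**4. Effect before knowing whether one occurs.** Let a fraction f of size-based responders also be PD. The documents do not give f, so it is an assumption. If PD takes precedence, the responder rate becomes p(1 − f), and the chance of success is P[Binomial(24, p(1 − f)) ≥ 7], ignoring early stopping.

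| f | p = 0.20 | p = 0.30 |
|---|---|---|
| 0 | 0.189 | 0.611 |
| 1% | 0.182 | 0.599 |
| 2% | 0.175 | 0.586 |
| 5% | 0.156 | 0.548 |
| 10% | 0.126 | 0.482 |
| 20% | 0.076 | 0.349 |

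**5. How much room the design leaves.** Entry requires M0 disease (Section 3.2.1). Metastatic progression at week 7 is already a treatment failure (Section 7.2.12). Table 4 places nephrectomy in week 13, and Section 7.3.1 calls proven disease after axitinib and surgery a recurrence. Route 1 therefore needs a patient with a good response in the kidney whose metastasis first appears around the week-12 scan and is then proven by biopsy. Route 2 needs the 41.7% shrinkage within seven weeks, regrowth of at least 20% in the next five, and one particular reading of the PD reference.

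**The case for a change.** The strongest case for a change is that the text does not settle the question. Section 5 applies RECIST 1.0 in the form it then lists, and the list has no ranking. Section 7.2.12 is confined to week 7. Section 6.1 says what happens to treatment after PD, not whether the patient can be a responder. The radiologist's reading settles who measures, not which class prevails, and the metastatic branch depends on a biopsy. The title favours counting the patient and the PD bullet favours not counting, while one sentence would cost nothing.

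The gap is real: week-12 precedence is unstated, and the PD reference is loosely worded. Three things limit its weight.

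- The week-7 rule and the removal of PD patients from treatment both point the same way, towards failure. An analyst who follows them would not credit a progressing patient as a responder.
- The other reading is not an error either. ORR measures activity in the kidney and PD measures harm. Section 6.1 monitors them as two counts, and a patient in both is not a contradiction.
- That such a patient may also be a disease-free survival event under Section 6.2.3 shows no fault. Any responder who later recurs is a success on one endpoint and an event on the other.

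The comparisons of 7/24 with 6/24 and of 2/18 with 1/18 show only that a cut-off is a cut-off. Any single disputed scan would have the same effect.

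**Conclusion.** No change to the plan follows. The classes overlap as written, but this is a missing detail with a sensible default in the plan's own handling of progression. The other reading, response of the primary tumour, is also defensible. The sample size, the cut-offs, the PD bounds, Tables 1 and 2 and the disease-free survival definition are the same under either.

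If such a patient occurs, the chance of declaring success differs by 0.15 to 0.19 between the two readings at true rates of 0.20 to 0.30 (0.305 − 0.160 = 0.145; 0.531 − 0.346 = 0.185; 0.731 − 0.560 = 0.171). Before that is known, the difference is at most about 0.025 if 2% of responders are affected (0.611 − 0.586) and 0.063 if 5% are (0.611 − 0.548), both at a true rate of 0.30. It would be material at 10% or 20%. The judgement therefore rests on the overlap being uncommon. The narrow window at week 12 supports that, but the documents give no rate to confirm it.
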